**The Feasibility, Usability, and Acceptability of Using the Oculus™
Virtual Reality Gaming Technology in Stroke Survivors for Upper Extremity and
Cognitive Rehabilitation**

NCT05672628

Version Date: 03/06/2024

Protocol Title: The Feasibility, Usability, and Acceptability of Using the Oculus™ Virtual Reality Gaming Technology in Stroke Survivors for Upper Extremity and Cognitive Rehabilitation

Principal Investigator: [name]

Co-Investigators: [name], DO; [name]; [name], OT; [name], SLP; [name]; [name] MD

Population: Stroke survivors and caregivers (n= 20 dyads) reflecting a range of stroke subtypes, disabilities, and races/ ethnicities will be recruited.

Number of Sites: 1 – Aging in Place (AIP) apartment, University of Texas Health Science Center at Houston

Study Duration: November 2022 – October 2023

General Information

- Primary Specific Aims (See Figure 1):
 - **S.A.1.** To test the (a) feasibility, (b) usability, and (c) acceptability of using the Oculus VR for chronic stroke survivors (6 months-5 years) who have mild-moderate cognitive and unilateral arm impairment to administer upper extremity and cognitive rehabilitation (n=20 dyads).-
 - **SA 2:** To calculate the change in upper extremity (Fugl-Meyer, ARAT) and cognition (MoCA) scores on standardized measurements per standard of care (n=20 dyads).
 - **S.A.3.** To qualitatively explore the impact of engaging caregivers in supporting the stroke survivor's rehabilitation and the impact of this engagement on the stroke survivor and caregiver dyad using semi-structured interviews. (n=20 dyads).
- Objectives:
 - Our overall objective in this application is first to determine whether Oculus VR is feasible, usable, and acceptable to stroke survivors who have chronic mild-moderate cognitive and upper extremity deficits. Our secondary objective is to explore the impact of the rehabilitation sessions using the Oculus VR on the caregiver-stroke survivor dyad

Background/Significance

- **A.1 Stroke Patients Need Long-term Upper Motor and Cognitive Rehabilitation.** Over half of stroke patients develop arm weakness post-injury.¹¹ A third to half of stroke patients develop cognitive impairment (CI) within the first 6 months of injury,^{2,3} and 1 in 5 stroke patients develop dementia.¹² These disabilities impact independence and impede returning to work. Stroke rehabilitation is the most important means for gaining functional recovery in stroke survivors.^{6,13} Chronic stroke survivors (\geq 6 months post-stroke) need upper extremity and cognitive therapies to prevent contractures and cognitive decline.⁶

- **A.2 Access to Stroke Rehabilitation is a Critical Health Care Problem.** In spite of the importance of stroke rehabilitation to functional outcomes, many stroke survivors have reduced access to stroke rehabilitation. More than half of all stroke survivors experience reduced mobility¹ and are often dependent on their caregiver for transportation. The average cost of outpatient stroke rehabilitation at \$17,000 during the first year after discharge from inpatient settings that is not covered by all forms of health insurance.⁷ Only a third of stroke survivors participate in outpatient stroke rehabilitation,¹³ and one study found that 57% of stroke survivors do not receive the recommended outpatient rehabilitation 6 months following discharge from inpatient facilities.⁸ Further, only 71% stroke patients who live in rural Texas have access to outpatient stroke rehabilitation services.¹⁴
- **A.3 Telerehabilitation Outcomes are Similar to Face-to-Face Rehabilitation.** Home-based stroke rehabilitation using telehealth technologies (e.g., telerehabilitation) increases access to stroke rehabilitation because it does not require transportation to a clinic, is accessible to stroke survivors who live in rural areas and is less costly¹⁵ than rehabilitation in the clinical setting. Studies have shown that stroke survivors who receive telerehabilitation have similar upper extremity⁹ and cognitive¹⁶ functional gains to those who received face-to-face rehabilitation.
- **A.4 Virtual Reality Enhances Stroke Rehabilitation Outcomes.** The VR gaming environment allows the user to interact with a computer-generated world.¹⁷ Studies have shown that stroke rehabilitation using gaming (e.g., Xbox) improves upper arm mobility^{18,19} and cognition.²⁰ Immersive VR using headsets allow the user to interact with and be fully immersed in a 3-D environment. A recent study used the HTC Vive headset in the clinical setting to deliver upper extremity stroke rehabilitation (n=12) who were 3 to 6 months post-stroke and found that there was significant improvement in arm mobility compared to stroke survivors who received standard of care (n=11; P<.05).²¹ However, the HTC Vive VR system is triple the cost of the Oculus VR and requires a computer and fixed sensors. Research is needed to determine the feasibility and usability of the Oculus VR for upper extremity and cognitive telerehabilitation in stroke patients.
- **A.5. Dual Tasking is a Novel Approach to Stroke Rehabilitation.** Combining motor and cognitive rehabilitation, known as dual-tasking, encourages neuro-stimulation and interaction between multiple brain regions. This is thought to promote neuroplasticity, the brain's ability to develop new neuronal connections and may lead to improved functional recovery.²² The use of cognitive stimulation in conjunction with physical exercise in older adults has been shown to improve episodic memory, visual attention, and functional mobility.²³ The Oculus VR is a novel way to promote dual-tasking for stroke rehabilitation.
- **A.6 Success of Remote Stroke Rehabilitation Depends on Caregiver Participation for Sustainability.** A significant barrier to stroke survivors accessing rehabilitation is the time burden and travel to appointments due to immobility, geographical distance, and caregiver work obligations.²⁴ During the COVID 19 pandemic, family caregivers of stroke survivors expressed uneasiness when unable to attend rehabilitation appointments due to COVID regulations.²⁵ Remote stroke rehabilitation may effectively address these barriers. Stroke survivors' motivation to engage in rehabilitation sessions has been shown to be positively influenced by positive reinforcement from the rehabilitation therapist.²⁶ Galvin and colleagues found that stroke patients (n=24) who received assistance/ feedback from a family caregiver during inpatient rehabilitation sessions had better motor outcomes than patients in the control group who did not receive input from a family member (n=20; P<.05).²⁷ Family members who participated during inpatient rehabilitation experienced lower caregiver stress than those in the control group (P<.01). Another study demonstrated that persons with dementia whose caregivers assisted with cognitive rehabilitation had improved memory as compared to the

control groups that did not involve caregivers.²⁸ Caregiver participation during rehabilitation may be essential for the sustainability of home-based cognitive and motor rehabilitation outcomes but has not been well-studied.

Population/ Sample Size

- Inclusion Criteria:
 - Ischemic, hemorrhagic, or subarachnoid hemorrhage (SAH) stroke diagnosis within 6 months to 5 years of enrollment. If the participant had a brain aneurysm then it must be secured. MRI report may be requested to confirm diagnosis or deficits as needed. Dyads will be included if they 1) are ≥ 18 years old; 2) can read, write, comprehend, speak English; and 3) are willing and able to provide informed consent. Caregivers must live in the home with the stroke survivor.
- Exclusion Criteria:
 - Stroke survivors will be excluded if they do not have score ranges that indicate mild to moderate severity on prior post-stroke neuropsychological tests, or the MoCA (15-25) using normative data based on education, age, and other standard demographic data, or other appropriate cognitive screening test selected by the speech language pathologist (also on this application) if the participant has aphasia, hemiopsia, other neurological or specific cognitive deficits, or demographic factors (e.g., education level) that prevents the participant from being accurately examined using MoCA or a modified MoCA; if cognition is within normal range then a FM (20-50), if they are unstable while standing unassisted, have a history of motion sickness/ vertigo/ dizziness/ seizures (a doctor's note will be requested for participants who do not believe their seizures will be triggered by the VR), claustrophobia, blind/deaf, and cannot hold the controller in their affected arm with or without the use of assistance.

Study Design/Methods

[figure not shown]

Figure 1: Study Schema

- Figure 1 depicts the overall study schema or flow as described below.

- Study Overview:
 - **S.A.1.** With the current drive for telerehabilitation and the advent of VR headsets, the examination of human factors perspectives is necessary before full implementation. End user perspectives regarding the impact, perceived usefulness, and perceived ease of use are essential, particularly in the older stroke population.
 - **S.A.2.** The rehabilitation team will measure changes on standardized measurements as part of standard of care.
 - **S.A.3.** Understanding the role of caregiver engagement upon stroke survivor rehabilitation outcomes and its potential impact on the quality of dyadic interpersonal relations is imperative for the sustainability of using VR for stroke rehabilitation in the home.
- Recruitment:
 - We will recruit 20 stroke survivor dyads (n=40) from the
 - Place: UT Physicians Department of Neurology Stroke Clinic, Brain and Behavioral Health Clinic, TIRR, Memorial Hermann, and Stroke Survivor Support Groups. In 2021, the clinic treated approximately 1000 stroke patients. Based on our knowledge of the clinic and previous experiences with stroke trial enrollment, enrolling 20 dyads over a 6-month recruitment period will be feasible. All rehabilitation sessions will take place in the Aging in Place (AIP) apartment.
 - Subjects meeting inclusion criteria will be offered participation incentives of \$100.00 (\$40 gift cards will be given at the first session and \$60 will be given at the final session) as well as parking reimbursement for each session to take place at the Cizik School of Nursing.
- Pre-Screening and Measurements:
 - Measurement objectives are to (1) determine study eligibility, (2) obtain demographic data, and (3) evaluate acceptability measures (4) assess perceived usefulness, ease of use, and attitude toward using the technology by conducting usability surveys and interviews. The informed consent document and quantitative measures will be available in English and accessible via REDCap.^{30,31}
 - Study personnel will determine if participants are cognitively able to consent by pre-screening participants with the following questions:
 1. *Have you/the participant ever been diagnosed by a doctor with dementia?*
 2. *Think about your/their abilities 10 years ago compared to the day before your/their stroke. Is your/their ability to make decisions on everyday matters better, the same, or worse?*
 - Please see Appendix A for the list of instruments and their psychometric data. See Figure 2 for primary and secondary outcomes and their timepoints.

Intervention

- The AIP apartment (See Appendix B) is a unique lab setting that simulates a real-world apartment. It is well-equipped with cameras to monitor the participant's rehabilitation session and their interaction with the therapist and caregiver and offers a typical living room with a smart television, an ideal setting for proof of concept of using the Oculus VR using the Job Simulator game (Appendix C) for remote stroke rehabilitation.
- Upon successful completion of this research, we expect our contribution to determine the

feasibility, usability, and acceptability of the Oculus VR for stroke rehabilitation in chronic stroke patients.

- This contribution is innovative because to the best of our knowledge no studies have evaluated the use of the Oculus VR in stroke patients stroke rehabilitation.
 - The Oculus VR engages two brain domains simultaneously and this may prove to be a novel and effective form of stroke rehabilitation.
- Our intervention has been developed in partnership with experienced stroke rehabilitation experts so that it can be easily implemented in any setting.
- We believe that this study will generate an estimate of the effect that can be used to inform the development of randomized controlled studies (RCTs).
 - This study will also generate RCTs examining the use of the Oculus VR as a form of stroke rehabilitation that is scalable to the participant's home setting.
 - There are few studies that have examined the role of caregiver engagement on the success of remote stroke rehabilitation.
- The caregiver will be encouraged to use Caregiver Cues (Appendix D) as this will help the caregiver to engage with the participant using encouragement or positive cues to the stroke participants to support them during the session.
- The therapist or RA (who will be trained by the therapist) who is conducting the session will use the Therapist Guided Cues (Appendix E) to guide the stroke participant with problem solving and planning for performing home exercises that will be provided to the participant at the first session.
- The data we obtain from caregivers and stroke survivors (dyads) will inform future studies that examine ways to best support the dyads to improve stroke rehabilitation outcomes and reduce stress in the caregivers. (See Appendix F)

Statistical Analysis

- To address S.A.1., feasibility, usability, and acceptability of the Oculus VR headsets for upper extremity and cognitive therapies will be analyzed as follows: Feasibility: Assessed from the number sessions attended and time spent using the Oculus VR. The minimum number of sessions expected for a user are 2 per week (8 sessions) and the minimum time spent playing Job Simulator is 1 hour per week (4 hours) through the end of the study. Descriptive statistics of the participation rates and measures including frequencies, median and interquartile ranges for sessions attended and time spent using the game. Usability: Descriptive statistics for demographic and clinical data and participant scores on the SUS and PQ will be calculated. (See Appendix G and H) We will refrain from using inferential statistics since this is a pilot study and hypothesis testing is not the objective. Acceptability: Descriptive statistics for scores on the SSQ will be calculated at baseline and after each session (See Appendix I). We will examine the trend of symptoms for each participant.)
- To address S.A.2. As part of standard of care, we will calculate change in arm and cognitive scores for each stroke participant from the following tests: MoCA, FM, and ARAT. (See Appendix J, K, and L) After inspection of the distribution, either the paired t-test or the nonparametric Wilcoxon signed rank test will be used to evaluate the significance of the difference score. However, statistical inference is not the primary interest of this pilot study. The effect size provided by Cohen's d measure, i.e., the standardized difference of mean score, will provide a preliminary measure of the effectiveness of Oculus VR in this pilot study. Similarly, standardized differences in the BSFC-s scores will provide the effect sizes for the change in caregiver burden.
- To address S.A.3., interview data will be analyzed following methods for thematic analysis.^{34,35} Using a qualitative data analysis program, Atlas.ti,³⁶ 2 researchers will review transcripts to gain a sense of the whole, identify codes, categories, and generate higher order themes to describe

the role of caregiver engagement during the session. Reasons for non-participation will be obtained from those eligible participants who decline participation. Unacceptable components and reasons for non-participation will be considered in the planning and designing of future trials.

Outcomes

- Upon completion of these aims, the expected outcomes are to develop randomized control trials (RCTs) to determine the effectiveness of the Oculus VR for stroke rehabilitation. We anticipate using the information from the dyadic interviews to develop qualitative studies and RCTs examining the role of the caregiver on remote stroke rehabilitation outcomes.
- Please see Table 1 (below) for the outcomes with timepoints.

Primary and Secondary Outcomes with Timepoints			
Primary	Timepoint	Secondary	Timepoint
MoCA (Appendix J)	Baseline and Last Session	Pre-Intervention Questionnaire (Appendix R)	Baseline Session
Fugl-Meyer (Appendix K)	Baseline and Last Session	Therapy Follow-Up Checklist (Appendix M)	Session 2 – Last Session
ARAT (Appendix L)	Baseline and Last Session	Post-Intervention Questionnaire (Appendix S)	Last Session
Caregiver Burden Scale (for caregiver only; Appendix F)	Baseline and Last Session		
Simulator Sickness Questionnaire (Appendix I)	Session 1 – Last Session		
System Usability Scale (Appendix G)	Last Session		
Presence Questionnaire (Appendix H)	Last Session		
Number of sessions attended; Duration (minutes) of session	Session 1 – Last Session		

Table 1

Potential Problems and Alternative Approaches

- If the participant cannot complete the study, then we will offer home exercises selected by the therapist from Appendix N and they will exit the study.
- Stroke survivors will be encouraged to take a brief break every 20 minutes due to potential for visual fatigue. If the participant develops simulator sickness (e.g., nausea, dizziness, etc.) or wishes to stop the session for any reason, we will immediately stop the session and allow the participant to rest until the symptoms subside.
 - If the participant's symptoms do not resolve immediately, then we will take the patient's blood pressure, pulse, and/ or temperature as appropriate.
 - We will call 911 should the participant require immediate assistance. If the participant does not require immediate care, we will encourage the participant to be evaluated at an urgent care and/ or their doctor's office.

- All adverse events will be monitored, documented, and reported to the ethics committees. Progress addressing adverse events will be recorded until their resolution.

Data Management

- We will record the Oculus gaming sessions using the camera located in the living room for the therapists to review after the session to evaluate the participants' progress.
- Informed consent documents and de-identified, demographic and participant satisfaction surveys will be stored electronically via REDCap,™ following UTHealth security procedures. Qualitative interview data will be digitally recorded; these raw audio files will be stored in a secure folder of the PI's UTHealth, OneDrive. Transcribed, de-identified interview data will be managed and analyzed via Atlas.ti.™

Collaboration and Interaction Plan

- The proposed interdisciplinary project brings together highly experienced investigators in diverse areas of research and clinical practices.
- The project is built from developing new collaborations between investigators across institutions including the University of Texas Health Science Center at Houston (UTHealth).
- The team will be led by

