Appendix Q
Timeline of Study Events with Outcome Measures and Timepoints

BASELINE (Video Call or in person)	Initial & Date completed
Informed Consent documents will be available in English. The consent form will be accessible via REDCap. This visit is to ensure the participant understands the basis of this voluntary study and provides consent to participate in the research study.	
Pre-First Visit (Video Call or in person at 1 st visit)	
We will ask the stroke survivor about their medical history and give the stroke survivor the Montreal Cognitive Assessment (MoCA) or other appropriate cognitive screening test if the participant has aphasia, hemiopsia, and other neurological deficits that cannot be examined using MoCA or a modified MoCA that will assess their cognitive capabilities. We will arrange a time to meet with the stroke survivor and their caregiver on a video call using the computer and this will take only 15 or 20 minutes. We will offer the option to complete the Pre-Intervention Questionnaire of the stroke survivor participant and Burden Scale for Family Caregivers depending on participant and caregiver preferences. This will take 15-20 additional minutes. F	

 1. Assess stroke survivor's medical history 2. Cognition (MoCA) test completed (Appendix J) 	
Inclusion Criteria	

Patients must meet the following criteria for study entry:
 
 • Ischemic, hemorrhagic, or SAH stroke diagnosis within 6 months to 5 years of enrollment. • Dyads will be included if they 
 ◦ Are \geq 18 years old ◦ Can read, write, comprehend ◦ Speak English ◦ Are willing and able to provide informed consent • Caregivers must live in the home with the stroke survivor. 	
Exclusion Criteria	
General	

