
 • Stroke survivors will be excluded if they do not have score ranges that indicate mild to moderate severity on prior post-stroke neuropsychological tests, or the MoCA (15-25) using normative data based on education, age, and other standard demographic data, or other appropriate cognitive screening test selected by the speech language pathologist (also on this application) if the participant has aphasia, hemiopsia, other neurological or specific cognitive deficits, or demographic factors (e.g., education level) that prevents the participant from being accurately examined using MoCA or a modified MoCA; if cognition is within normal range then a FM (20-50) • Have a history of: 
 ◦ Motion sickness ◦ Vertigo ◦ Dizziness ◦ Seizures (a doctor's note will be requested for participants who do not believe their seizures will be triggered by the VR) ◦ Claustrophobia ◦ Blind/deaf • Cannot hold the controller in their affected arm. 	

	IRB NUM: ER: HSC-SN-22-08 8
	IRB APPROVAL DATE: 03/06/2024

1st Session (Week 1)	Initial & Date completed

3. Pre-Intervention Questionnaire will be given during the first session. (Appendix R)
 
4. Cognition (MoCA or other appropriate) test completed (if not completed during pre-first visit) (Appendix J)
 
5. Fugl-Meyer Upper Extremity Assessment (Appendix K)
 
6. Action Research Arm Test (ARAT) (Appendix L)
 
a. 3,4, and 5 will be completed as a part of standard of care.
 
7. Burden Scale for Family Caregivers – short version will be given to the caregivers of the stroke subjects via REDCap. (Appendix F)
	
 Recruit from stroke units/clinics	
 Study coordinator screens for eligibility requirements	
 Obtain Informed Consent Documents from Dyads	
 Complete the Cognition (MoCA) test (pre-intervention) (Primary Outcome; Appendix J)	
 Complete the Fugl-Meyer Upper Extremity Assessment (pre-intervention) (Primary Outcome; Appendix K)	
 Complete the Action Research Atm Test (ARAT) (pre-intervention) (Primary Outcome; Appendix L)	
 Have the Caregivers complete the Burden Scale for Family Caregivers (Primary Outcome; Appendix F)	

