We will give the stroke survivor the Montreal Cognitive Assessment (MoCA) that will assess their cognitive capabilities. We will arrange a time to meet with them on a video call using the computer and this will take only 15 or 20 minutes.	
1. Cognition (MoCA) test completed (Primary Outcome; Appendix J)	
12th Session (Week 4, last session; in the event that the study participant and/ or caregiver are unable to complete any post-intervention items, we will request a video call to complete any missing items that were not completed on the last session at a time convenient to the stroke participant or caregiver)	Initial & Date completed

 _____ Research Assistant complete the Therapy Follow Up Checklist with Subject before the start of the session. (Secondary Outcome, Appendix M) _____ Have the stroke survivor complete the Simulator Sickness Questionnaire (SSQ) at the beginning and end of the last 1-hour session (Primary Outcome; Appendix I) _____ Complete the System Usability Survey (SUS) via REDCap (Primary Outcome; Appendix G) _____ Complete the Presence Questionnaire (PQ) (Primary Outcome; Appendix H) 	

 Complete the Cognition (MoCA) test (post-intervention, if not completed during the Pre-Last Visit) (Primary Outcome; Appendix J)	
 Complete the Fugl-Meyer Upper Extremity Assessment (post-intervention) (Primary Outcome; Appendix K)	
 Complete the Action Research Atm Test (ARAT) (post-intervention) (Primary Outcome; Appendix L)	
 Complete the Caregiver Burden Questionnaire (Primary Outcome; Appendix F)	
 Complete the Post-Intervention Questionnaire (Participant and Caregiver) (Secondary Outcome; Appendix S)	

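### Another cognitive test, or a modified MoCA, is allowed at baseline, but the pre-last visit instruction and the change-score analysis name only the MoCA

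*Combined protocol and SAP*

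**What the plan says.** All references are to the combined protocol and SAP.

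**Baseline.** The Exclusion Criteria accept the MoCA "or other appropriate cognitive screening test selected by the speech language pathologist" where the person has aphasia, visual field loss, another deficit or a demographic factor "that prevents the participant from being accurately examined using MoCA or a modified MoCA". Appendix Q repeats the criterion. Its Pre-First Visit text provides for the MoCA "or other appropriate cognitive screening test if the participant has aphasia, hemiopsia, and other neurological deficits that cannot be examined using MoCA", and item 4 of the 1st Session reads "Cognition (MoCA or other appropriate) test completed (if not completed during pre-first visit".

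**End of study.** The Pre-Last Visit text in Appendix Q reads "We will give the stroke survivor the Montreal Cognitive Assessment (MoCA) that will assess their cognitive capabilities". The 12th Session line reads "Complete the Cognition (MoCA) test (post-intervention, if not completed during the Pre-Last Visit". Neither mentions a substitute or a modified form.

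**Analysis.** The S.A.2 paragraph of Statistical Analysis says change will be calculated for each stroke participant and lists the MoCA, Fugl-Meyer (FM) and ARAT. It then calls for a paired t-test or Wilcoxon signed rank test, and Cohen's d. Table 1 lists the MoCA as a primary outcome at baseline and last session. Appendix A describes only the MoCA as the cognitive assessment. No section says what to do with a participant whose baseline was another test.

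**The concern.** A change score needs the same instrument at both ends. The plan permits departures from the MoCA at baseline and then directs the MoCA at the end. A participant who could not be examined accurately on the MoCA would finish on the test the plan regards as inaccurate for them, with no MoCA baseline to subtract.

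Those affected would not be a random few. They are people with aphasia, visual field loss, other specific deficits, or an educational or demographic background that makes the MoCA unsuitable. The cognitive result would omit or mis-measure them. This matters even in a pilot, because the Intervention section says the effect estimate will inform randomized trials. A final assessment made on the wrong instrument cannot be repaired in the analysis.

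**Working it through.** The plan states 20 dyads with no alpha, power, SD or effect size, so there is no calculation to reproduce. The check is mainly a comparison of texts, followed by one precision calculation.

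**Step 1. Which texts allow another test, and which name only the MoCA.**

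| Place | Time | Test named |
|---|---|---|
| Exclusion Criteria (repeated in Appendix Q) | Entry | MoCA or another test; a modified MoCA is implied |
| Appendix Q, Pre-First Visit sentence | Baseline | MoCA, modified MoCA or another test |
| Appendix Q, Pre-First Visit, item 2: "Cognition (MoCA) test completed (Appendix J" | Baseline | MoCA |
| Appendix Q, 1st Session, item 4 | Baseline | MoCA or another test |
| Appendix Q, 1st Session checklist: "Complete the Cognition (MoCA) test (pre-intervention" | Baseline | MoCA |
| Appendix Q, Pre-Last Visit sentence | End | MoCA |
| Appendix Q, 12th Session line | End | MoCA |
| Statistical Analysis, S.A.2 | Change score | MoCA |
| Table 1; Appendix A | Baseline and end | MoCA |

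**Step 2. Which rows count as evidence.** Item 2 of the Pre-First Visit uses the MoCA-only label directly after a sentence that allows another test. The 1st Session checklist uses it although item 4 of the same visit allows another test. The label can therefore be shorthand, and the 12th Session line may be shorthand too. These three lines are set aside.

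The Pre-Last Visit sentence is different. It is a full sentence that matches the Pre-First Visit sentence in purpose, spells out the instrument's name, and lacks the substitute clause. S.A.2, Table 1 and Appendix A also name the MoCA without any alternative.

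**Step 3. Trace each kind of participant through the plan as written.**

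- Full MoCA at baseline: full MoCA at the end. The pair is valid.
- Modified MoCA at baseline: MoCA at the end, form not stated. The pair may mix two forms.
- Substitute at baseline: MoCA at the end. There is no valid change on either test, yet S.A.2 calls for one.

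**Step 4. Effect on precision if pairs are lost.** The 95% half-width for a mean paired change, in units of the SD of change, is t(0.975, n − 1)/√n. The documents give n = 20. The smaller values are assumptions (2 or 5 participants without a valid MoCA pair).

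- n = 20: 2.093/4.472 = 0.468
- n = 18: 2.110/4.243 = 0.497
- n = 15: 2.145/3.873 = 0.554

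Losing 5 of 20 pairs widens the half-width by 0.554 − 0.468 = 0.086 SD. The loss is mainly in who is represented.

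**The case against.** The strongest reply is that this is shorthand. Appendix Q uses the MoCA-only label at baseline, where another test is plainly allowed, and the S.A.2 entry in the Study Overview speaks only of standardized measurements. That stands for the checklist lines, which is why they are not relied on. It does not explain why the Pre-Last Visit sentence lacks the clause its counterpart carries, or why the S.A.2 analysis has no rule for a non-MoCA baseline. If shorthand was meant, a few words settle it.

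It can also be said that same-form pairing still leaves these participants out of the MoCA result. That is correct. What repetition gains is a valid change on their own test, which is otherwise lost, and a MoCA result that contains only MoCA pairs.

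The number affected may be zero, and the plan says inference is not its primary interest. Both are true. They limit the urgency but do not remove the defect in a listed primary outcome.

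Two stronger readings are tempting, and the documents support neither:

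- A reader might infer that mixed forms inflate the mean change or d by some stated amount. The plan does not define the modified MoCA, its scoring, or whether a full form follows it, so any figure would rest on an invented scenario.
- A reader might infer that the pooled d is invalid because entry requires FM 20-50 only when cognition is normal, while S.A.1 describes both deficits. S.A.2 carries no two-deficit wording, d is a legitimate summary of those enrolled, and individual changes are calculated and can be broken down. What remains is a wording mismatch.

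**Conclusion.** The point holds. The baseline provisions and the end-of-study and analysis provisions for cognition do not fit together. Followed literally, they give a participant with a substitute baseline no valid cognitive change score, and may give one with a modified MoCA a mixed-form pair. The conclusion rests on reading the Pre-Last Visit sentence and S.A.2 as written, and it does not depend on the checklist labels.

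Its size cannot be fixed from the documents, because the number of substitute or modified tests is not given. Under the assumed counts the loss of precision is modest. The more serious effect is the selective loss of a defined group. The correction is worth making because it is nearly free and the missing final assessment cannot be obtained later.

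As a separate, minor matter, the S.A.1 and overall objective wording (cognitive and arm deficits together) and the either/or entry rule describe different groups and need to be reconciled.

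**What to change.** 1. Reconcile the S.A.2 analysis, Table 1, Appendix A and the 1st Session, Pre-Last Visit and 12th Session entries of Appendix Q with the Exclusion Criteria and the Pre-First Visit text. State that the cognitive test and form used at baseline are recorded and repeated at the end, in place of the MoCA for that person.
2. State that MoCA change and its Cohen's d are computed only from MoCA pairs on the same form, with n. Report changes on substitute tests separately and descriptively, with n for each test.
3. Reconcile the S.A.1 and overall objective wording with the entry rule in the Exclusion Criteria and Appendix Q.

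**Cost.** A few lines of text and one data field. The repeated test replaces the final MoCA, so no procedure is added. The MoCA n may fall below 20, with the half-widths shown above. Substitute tests chosen person by person may not combine into one summary. The documents do not say whether final visits are already complete. If they are, item 2 still applies, and the number of participants without a valid pair should be reported.
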